Baseline to Week 48: Patients will receive intradermal injection of study medication once per month to all, or as many as possible, areas of hair loss up to the maximum dose of 30mg IL TAC per month, for a total of 6 months. Injections will be performed at baseline, weeks 4, 8, 12, 16 and 20. Injection areas will be chosen based on the investigator's clinical assessment of factors including but not limited to, areas of most active shedding, areas of maximum medical and cosmetic benefit, avoidance of any areas of pre-existing atrophy, etc. Patients will be seen at weeks 28, 32, 36, 40, 44 and 48 after end of treatment in order to assess the frequency and timing of relapse. Nonresponders to 6 months study treatment (defined as failure to achieve 50% improvement in SALT score at week 24 compared to baseline) will not be required to participate in the 6 month follow-up period but will be given the option of receiving monthly IL TAC 2.5mg/ml, 5mg/ml or 10mg/ml injections for 6 months if deemed appropriate by the investigator. The dosage to be utilized (2.5mg/ml vs. 5mg/ml vs. 10mg/ml) will be based on clinical considerations, unless study data is available to support preference of one dose versus the other. Patients identified by unblinded study personnel as having received TAC or with obvious signs of atrophy or other indications suggesting they have already been treated with active drug for 6 months will not be given the option of continuing IL TAC as it is unlikely that they will respond if they have not responded by 6 months unless available evidence suggests that utilization of a different dosage is more likely to be efficacious and safe.

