Week 24 +/- 7 days – End of treatment also end of study for nonresponders not continuing on to open label treatment and beginning of open label treatment for nonresponders continuing to open label treatment

- Vital signs, body weight
- Physical and dermatological examination
- Adverse events reporting, concomitant medication review
- Photography
- Physician evaluation utilizing the PGA and SALT scale
- Patient global assessment and quality of life assessment
- Urine pregnancy testing
- Clinical laboratory evaluation
- Optional scalp biopsy (4mm punch biopsy) and blood collection for immunological studies
- IL TAC injection for qualified nonresponders continuing to open label treatment

Weeks 28, 32, 36, 40, 44 and 48 +/- 7 days– Observational Period for responders or IL TAC Injection period for nonresponders deemed appropriate for open label injection

- Vital signs, body weight

- Physical and dermatological examination (only week 48)
- Adverse events reporting, concomitant medication review
- Photography (weeks 36 and 48)
- Physician evaluation utilizing the PGA and SALT scale
- Patient global assessment
- Patient quality of life assessment (only weeks 36 and 48)
- Optional Scalp biopsy (4mm punch biopsy) at additional timepoints at the discretion of the principal investigator and with the consent of the subject, based upon perceived utility in context of individual patient response to therapy and durability of that response.
- Optional Blood collection for immunological studies at additional timepoints at the discretion of the principal investigator and with the consent of the subject.
- IL TAC injection for qualified nonresponders.

Early Termination

- Vital signs, body weight
- Physical and dermatological examination
- Adverse events reporting, concomitant medication review
- Photography
- Physician evaluation utilizing the PGA and SALT scale
- Patient global assessment and quality of life assessment
- Clinical laboratory evaluation
- Scalp biopsy (4mm punch biopsy) – if indicated and if patient agreeable to biopsy and 2 week f/u for suture removal if deemed necessary.
- Blood collection for immunological studies

Unscheduled Visits

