As secondary endpoints, efficacy will be measured by changes in hair re-growth as a continuous variable as determined by physical exam and Canfield photography, as well as patient and physician global evaluation scores. To assess the durability of responses, patients who achieve 50% reduction in baseline SALT score will continue to be followed for an additional 6 months off treatment.

Secondary efficacy outcomes will include:

1. Percent hair regrowth from baseline determined by SALT measurements following 12, 24 weeks of treatment and at weeks 36 and 48 following discontinuation of treatment (Price et al Efalizumab study)
2. Comparison of the proportion of responders in each group, with response defined as 50% change in SALT score (50% regrowth) from baseline, at weeks 12, 36 and 48.
3. Comparison of the proportion of subjects in each group attaining global overall improvement SALT score of A5 (100% coverage) supported by </= SALT 25 at weeks 12, 24, 36 and 48.
4. Change in PGA (Physician global assessment) based on evaluation of live evaluations and standardized photographs between baseline, week 12, 24, 36 and 48
5. Change in patient global assessment (100mm Visual analogue scale) between baseline, Week 12, 24, 36 and 48
6. Change in patient quality of life assessment (DLQI or DQLS) from baseline to weeks 12, 24, 36 and 48. (Finlay and Khan 1994).
7. Frequency of occurrence and timing of relapse (as defined above) in responders followed for 6 months off therapy.

Safety and tolerability measures:

Incidence and severity of adverse effects (AEs) including the presence and degree of skin atrophy.

Incidence of treatment-emergent laboratory abnormalities.

Sample size

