Power analysis is based on a chi-squared test of proportions of responders in the 4 study groups, where response is defined as 50% reduction in SALT score. Effect size is quantified in terms of Cohen's w , a function of the response rates in the fourgroups (15). A minimal treatment effect size of 40% (Cohen's $w = 0.4$) i.e. a 50% response rate for active drug (IL TAC 2.5mg/ml, 5mg/ml or 10mg/ml) versus a presumed spontaneous remission response rate of 10% for patients receiving inactive IL saline, would be considered clinically meaningful in this study. To achieve 80% power to detect the desired effect size of 40% with a usual 5% level of significance (alpha), we would require approximately 17 subjects per arm (68 subjects in total). With this sample size, an effect size of 50% (Cohen's $w = 0.5$, "large" effect) would ensure approximately 95% power. Our postulated effect size for IL TAC is based on impressions due to clinical use of IL TAC in AA, however an explicit aim of this pilot study is to objectively and more precisely quantify the actual treatment effect of the various doses of IL TAC versus saline placebo.

Data Analysis Plan

The primary analysis will be a comparison of response rates in the 4 study groups, using a chi-squared test of proportions. If the 4-group comparison is significant, we will compare the efficacy and safety profiles of the three doses of intralesional triamcinolone head to head. For secondary outcomes that are binary (response/non-response), we will follow the same strategy. For secondary outcomes that are continuous (e.g. change in SALT measurement or PGA), we will conduct 4-group ANOVA tests, followed by pairwise

comparisons, if necessary. In both cases, Bonferroni correction will be made to adjust for multiple testing. To assess safety, we will summarize and test the incidence rates of adverse events across groups.

If possible, we will attempt to stratify the patients based on baseline degree of hair loss e.g. 0-25% vs. 26-50% hair loss in order to assess if response is correlated with degree of hair loss present at baseline. (Olsen E. Investigative guidelines for alopecia areata.

Dermatologic therapy 24, 2011 311-319

All outcomes will be analyzed on the intent to treat (ITT) basis.

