An AE is any unfavorable and unintended sign, symptom, or disease temporally associated with the use of a study medication(s), whether or not related to the study medication(s). AEs that occur after randomization should be recorded on the AE page of the CRF. Recording should be done in a concise manner using standard, acceptable medical terms. The AE recorded should not be a procedure or a clinical measurement (i.e., a vital sign), but should reflect the reason for the procedure or the diagnosis based on the abnormal measurement. Any clinically significant changes in pre-existing conditions (based on medical history/physical examination results) will be recorded on the CRF AE pages. The intensity of all AEs should be classified as follows:

Mild: A mild AE is defined as an event characterized by "awareness of symptoms which are easily tolerated."

Moderate: A moderate AE is defined as an event in which "sufficient discomfort is present to cause interference with usual activity."

Severe: A severe AE is defined as an event characterized by "extreme distress causing significant impairment of function or incapacitation."

A serious adverse event (SAE) is any AE occurring at any dose that results in:

- Death
- A life-threatening event
- Inpatient hospitalization or prolongation of existing hospitalization
- Persistent or significant disability/incapacity
- Congenital anomaly/birth defect.

In addition, an important medical event that may not result in death, be life-threatening, or require hospitalization may be considered an SAE when, based on appropriate medical judgment, it may jeopardize the patient and/or may require medical or surgical intervention to prevent one of the outcomes listed above.

An unexpected AE is any AE of which the specificity or severity is not consistent with the current Investigator Brochure/Package Insert. A reasonably related AE is one that is possibly, probably, or definitely related to study medication (as determined by the study investigator).

Immediate Reporting by Investigator

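### The between-group adverse-event test has no time window, so events from open-label IL TAC after week 24 can be counted as saline events

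*Combined protocol and SAP*

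**What the plan says.** The Data Analysis Plan gives one sentence on safety: "To assess safety, we will summarize and test the incidence rates of adverse events across groups". The same section adds: "All outcomes will be analyzed on the intent to treat (ITT) basis". Under Study outcomes, the safety measures begin with "Incidence and severity of adverse effects (AEs) including the presence and degree of skin atrophy", followed by treatment-emergent laboratory abnormalities. None of these has a time window, and treatment-emergent is not defined.

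Collection is long. Adverse Event Reporting states: "AEs that occur after randomization should be recorded on the AE page of the CRF", with no end date. The Schedule of Assessments marks adverse events at every visit from baseline to week 48.

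Treatment changes at week 24. Under Baseline to Week 48, non-responders "will be given the option of receiving monthly IL TAC 2.5mg/ml, 5mg/ml or 10mg/ml injections for 6 months if deemed appropriate by the investigator". Patients identified as already given active drug, or showing obvious atrophy, are by default not offered this, unless evidence favours a different dosage. The week 24 visit is "also end of study for nonresponders not continuing on to open label treatment". Weeks 28 to 48 are headed "Observational Period for responders or IL TAC Injection period for nonresponders deemed appropriate for open label injection".

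The Data Analysis Plan and the Data and Safety Monitoring Plan also allow open-label active drug for all patients after the 3-month interim look, if efficacy is shown and safety is acceptable.

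No section sets a cut-off for the safety comparison, says to which arm an event after a switch belongs, or plans a separate open-label safety summary.

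**The concern.** The randomised contrast between IL TAC and saline exists only while saline patients receive saline. After week 24 the patients most likely to start IL TAC are those randomised to saline, because most of them are expected to be non-responders and the default bar on further IL TAC does not apply to them. If all collected events are analysed by randomised arm, atrophy that appears on open-label steroid is credited to saline. The saline incidence rises and the contrast shrinks.

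What is at stake is the trial's evidence on whether IL TAC causes atrophy. Atrophy is a named safety measure, and with 17 patients per arm there is little room to lose contrast. After screening, the scheduled physical and dermatological examinations, apart from early termination, fall at weeks 24 and 48. Whether the week-48 findings enter the comparison is therefore a substantive choice, and the plan does not make it.

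**Working it through.** **Plan's own figures.** The documents give no number for the safety comparison. The stated power for the four-group response test is reproduced: noncentral chi-squared, 3 degrees of freedom, noncentrality 68 × 0.4² = 10.88, gives 79.9% against the stated 80%. With w = 0.5, 68 × 0.5² = 17 gives 94.8% against about 95%. The four-group power figures below use the same method.

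**Inputs from the Sample size section.** 17 patients per arm and a 10% saline response, so 17 × 0.9 = 15.3 saline patients are expected to be non-responders at week 24.

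**Assumed inputs.** r is the atrophy risk over six months of IL TAC, and u is the share of saline non-responders who are offered open-label IL TAC and take it. The risk on saline itself is first set to 0, and no new atrophy is added in the steroid arms after week 24. The documents give neither r nor u.

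**Formula.** If events to week 48 are counted by randomised arm:
- saline incidence = 0.9 × u × r
- difference = r − 0.9 × u × r = r × (1 − 0.9u)

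With r = 20%, the difference during the blinded period is 20 points. To week 48:

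| Uptake u | Saline patients switching (15.3 × u) | Saline atrophy (0.9 × u × 20%) | Difference |
|---|---|---|---|
| 25% | 3.8 | 4.5% | 15.5 points |
| 50% | 7.65 | 9% | 11 points |
| 100% | 15.3 | 18% | 2 points |

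**Other assumed rates.** Let the 24-week risk be q0 on saline and q1 on IL TAC. Saline incidence to week 48 is q0 + (1 − q0) × 0.9 × u × q1. With q0 = 5% and q1 = 40%, the blinded-period difference is 35 points and four-group power is 61%. To week 48:
- u = 50%: saline 5% + 0.95 × 0.9 × 0.5 × 40% = 22%, difference 18 points, power 18%
- u = 75%: saline 31%, difference 9 points, power 8%
- u = 100%: saline 39%, difference 1 point, power 5%

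Over q0 of 2-5%, q1 of 20-50% and u of 50-100%, blinded-period differences of 15 to 48 points become −2 to 26 points.

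**Person-time.** With responders followed for the full 48 weeks, the share of saline-arm time spent on IL TAC is (0.9 × u × 24) / (24 + 0.1 × 24 + 0.9 × u × 24):
- u = 25%: 5.4 / 31.8 = 17%
- u = 50%: 10.8 / 37.2 = 29%
- u = 100%: 21.6 / 48 = 45%

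Reporting events per person-time would therefore not remove the problem.

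**The case against.** The strongest reply is that the plan never says the adverse-event test runs to week 48. Collection to week 48 is a visit schedule, not an analysis period. Week 24 is labelled end of treatment, and open-label injections have their own row in the schedule. A week 0-24 comparison fits the text and would be free of this bias unless the interim look opens the trial early. This stands: a reader might infer that the plan commits to counting open-label steroid harm in the saline arm, and it does not. But it does not commit to the alternative either, and the two readings can give very different answers.

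A second reply is that ITT is meant for efficacy, since safety items are called measures rather than outcomes. They do sit under the Study outcomes heading, however, and the ITT sentence covers all outcomes. If it does not reach adverse events, no attribution rule is left.

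A third is that the size rests on assumed inputs. That is correct. Open-label drug is optional and at the investigator's discretion, so the 2-point result, which needs every saline non-responder to switch, is an extreme. At 25% uptake the loss is 4.5 of 20 points.

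Finally, routine laboratory tests largely stop at week 24. Week 28 is only if needed, and optional cortisol at weeks 28 and 48 is the main exception. The cut-off therefore changes little for laboratory data.

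**Conclusion.** The point holds as an unspecified safety window combined with an as-randomised rule. Applied to all collected events, the written rules attribute open-label steroid events to saline and dilute the steroid-saline contrast. At an assumed 20% atrophy on IL TAC and 0% on saline, a 20-point difference becomes 15.5, 11 or 2 points at 25%, 50% or 100% uptake. Only the 15.3 of 17 rests on the plan's own figures. This should be fixed, but it does not affect the primary efficacy analysis.

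Three further inferences are tempting, and the documents do not support them:

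- **Bias from both sides.** A reader might infer that early departure of steroid non-responders also lowers the steroid incidence. In the calculation all the shrinkage comes from the saline arm. The observation time lost in the steroid arms would have been off drug.
- **Unequal follow-up.** At the plan's 50% response, 17 × 0.5 = 8.5 patients per steroid arm would by default leave at week 24. Saline non-responders who decline or are not offered open-label drug leave too: 17 × 0.9 × 0.5 = 7.65 at 50% uptake, close to 8.5. At 25% uptake, 17 × 0.9 × 0.75 = 11.5 leave, which is more than in a steroid arm. A one-sided imbalance appears only at high uptake.
- **A blurred dose comparison.** Open-label drug goes mainly to saline patients, who are outside the head-to-head comparison of strengths. Blurring would need frequent use of the different-dosage exception, and nothing indicates that.

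**What to change.** In the Safety and tolerability measures and the Data Analysis Plan, state that:

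1. The between-group comparison of adverse events, atrophy and laboratory abnormalities is by randomised arm. It covers events with onset from the first blinded injection to the week-24 visit, before any open-label injection at that visit.
2. A patient who starts open-label drug earlier, including after the 3-month interim look, is censored at the first open-label injection.
3. Later events are reported descriptively in two separate tables: open-label patients by strength actually received, and off-treatment responders by original arm. Neither is pooled with the randomised comparison.

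The cost is plan wording, with no extra visits or patients and no change to treatment. The analysis needs an onset date for each event and the date of the first open-label injection. The documents do not list the fields of the adverse-event page, so confirm that it carries the onset date. The downside is that late events are described rather than tested between arms. This includes any atrophy from the last blinded injections that first shows after week 24.

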in which fewer than 10% are expected to achieve this magnitude of hair regrowth spontaneously. In contrast, clinical experience would suggest that approximately 50% of subjects treated with either dose of IL TAC may achieve $\geq 50\%$ improvement in SALT score after 6 months of treatment. The goal of this study is to validate or refute this clinical impression and to objectively and precisely quantify the treatment effect of 2.5mg/ml, 5mg/ml or 10mg/ml of IL TAC in AA.

Subjects will be randomized 1:1:1:1 to the placebo or treatment arms, and will receive 6 months of treatment with the study medication or placebo. IL TAC 2.5mg/ml, 5mg/ml, 10mg/ml or placebo will be administered at baseline, then every 4 weeks thereafter for 5 cycles (weeks 4, 8, 12, 16, 20) for a total treatment period of 6 months. Percent hair regrowth from baseline will be determined by SALT measurements following 4, 8, 12, 20 and 24 weeks of treatment. Punch biopsies and peripheral blood will be obtained at baseline prior to treatment, and then once again at a time point between weeks 4 and 20, to be determined by the investigator as indicated by clinical considerations such as variation in the timeline to regrowth from one subject to another, for immunomonitoring/biomarker studies. Additional, optional scalp biopsies and blood draws may be taken at other key time points in order to monitor response to therapy at the discretion of the investigator and with the consent of the study subject. Efficacy will be measured by change in hair re-growth as determined by physical exam and photography, as well as by patient and physician global evaluation scores. Physician and patient global evaluation scores will be determined based on the use of similar 100mm Visual Analogue scales with 0 labeled as no scalp hair loss and 100 labeled as complete scalp hair loss. Patients and physicians will place a vertical mark along the horizontal line depending on their assessment of the degree of hair loss present at the time of assessment.

As secondary endpoints, efficacy will be measured by changes in hair re-growth as a continuous variable as determined by physical exam, SALT score and Canfield photography, as well as patient and physician global evaluation scores.

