A 3-month interim analysis of the primary and secondary outcomes will be performed by an independent group in order to determine if statistical significance has been attained. A Haybittle-Peto rule for alpha spending (Haybittle 1971; Peto et al. 1976) will be followed for the interim analysis. If statistical evidence of efficacy is attained at 3 months and if the safety profile is acceptable, all patients will be offered the option of receiving open label active drug for the remaining duration of the trial.

To compare the frequency of occurrence of relapse in responders (followed for 6 months off therapy) across the four groups, we will employ a chi-squared test for comparing multiple proportions.

Furthermore, to compare the timing of relapse in responders (followed for 6 months off therapy) across the four groups, we will use tools from survival analysis (or, time-to-event analysis, with relapse as the event of interest). More specifically, first, we will conduct a descriptive analysis by graphically comparing the Kaplan-Meier survival (time-to-relapse) curves for the four groups. Next, we will use the log-rank test to formally test the null hypothesis of no difference between the survival functions of the four groups.

Specific Aim 2. To identify a clinical correlation between treatment outcome and down modulation of key AA-associated immunohistopathological markers and biomarkers in the treated skin; including NKG2DL expression in the hair follicle, immune infiltration (CD8⁺NKG2D⁺ cells) and expression of interferon response genes.

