Each year the Dermatology Department at CUMC sees 600 AA visits each year. Of these we expect roughly 20 to 30% to be eligible for this study of mild to moderate patch type alopecia. We also have a database of almost 400 patients evaluated at CUMC as part of the alopecia areata registry who have expressed an interest in being contacted for clinical trials in alopecia areata. In addition, we hope to have information regarding the study posted on the website for the National Alopecia Areata Foundation (NAAF) the largest AA patient advocacy organization. We expect to complete accrual of 68 patients within the 1 to 2 year study period (38 patients at CUMC and 30 at the University of Minnesota). This time frame will enable 6 months on treatment and 6 months follow-up off drug (for patients who qualify) and completion of the clinical correlative portion of the study

Assessment of Safety

Safety precautions such as the use of highly experienced investigators, frequent visits, and close monitoring of clinical and laboratory findings have been implemented in the protocol and are specified in the Schedule of Assessments. Hematology and chemistry measurements, including WBC count, platelet and absolute neutrophil counts, urinalysis and hepatic panel may be obtained at screening and at other time points if deemed necessary by the investigator.

All physical examination findings, vital sign abnormalities, and clinical laboratory abnormalities, will be captured as AEs when deemed medically significant by the investigator. A qualified physician associated with the study will be available to assess clinical signs and symptoms that may be indicative of an adverse event. Safety will be assessed by

summarizing the incidence and type of AEs. The proportion of patients who discontinued treatment will be summarized.

Methods and Timing of Safety Assessments

Adverse Event Reporting

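### Adverse-event incidence is to be significance-tested across four arms of 17 with no interval planned, and a non-significant result cannot show that the strengths are equally safe

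*Combined protocol and SAP*

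**What the plan says.** The Data Analysis Plan has one sentence on safety inference: "To assess safety, we will summarize and test the incidence rates of adverse events across groups". It does not name the test. Earlier in the same section, after the four-group comparison of response rates and conditional on that comparison being significant, it says "we will compare the efficacy and safety profiles of the three doses of intralesional triamcinolone head to head". A Bonferroni correction is stated for the binary and continuous outcomes; whether it extends to adverse events is not said.

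The Assessment of Safety section is descriptive: safety is assessed by "summarizing the incidence and type of AEs", and discontinuations are also summarised. The safety and tolerability measures include whether skin atrophy is present and to what degree.

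The Sample size section works from SALT response only: "we would require approximately 17 subjects per arm (68 subjects in total"). No section gives an expected adverse-event or atrophy rate, a power for safety, or a confidence interval for any safety measure.

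Safety findings feed a decision. In the interim paragraph of the Data Analysis Plan, if efficacy is shown at 3 months and "if the safety profile is acceptable, all patients will be offered the option of receiving open label active drug". The introduction presents the relative safety of the different strengths as a question that no well-designed randomised trial has examined.

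**The concern.** A test of incidence in four groups of 17 gives a p-value and nothing about how large a harm the data leave open. If the p-value is above 0.05, a report can easily drift into saying that the strengths were similarly tolerated, or no worse than saline, when the data are compatible with a large difference. The plan neither calls for an estimate with an interval nor warns against that reading.

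The between-strength safety comparison is also tied to the wrong gate. As written, it follows only from a significant four-group comparison of response. If response does not differ significantly, no comparison of the strengths on safety is planned, although that question does not depend on efficacy.

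At stake are the trial's answer on dose and safety, and the quality of the safety evidence available when open-label active drug is considered.

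**Working it through.** **Inputs.** From the documents: four arms, 1:1:1:1, 17 per arm, two-sided alpha 0.05 (stated for efficacy, assumed here for the safety test). Assumed: all event rates, because the documents give none, and a Pearson chi-squared test with 3 df, because the safety test is not named.

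**1. The plan's own figure (efficacy).** Power = P(noncentral chi-squared, 3 df, noncentrality N·w² > 7.81). With N = 68: w = 0.4 gives 79.9% and w = 0.5 gives 94.8%. The stated 80% and about 95% reproduce. They apply to SALT response and say nothing about adverse events.

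**2. Precision, with no assumed event rate.**

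- *Zero events in one arm.* The one-sided 95% upper limit is 1 - 0.05^(1/17) = 16.2%. The two-sided exact limit is 1 - 0.025^(1/17) = 19.5%.
- *4/17 against 1/17.* The difference is 3/17 = 17.6 points and the pooled rate is 5/34. Chi-squared = (3/17)² / [(5/34)(29/34)(2/17)] = 0.0311/0.0148 = 2.11, below 3.84, so non-significant.
- *Newcombe 95% interval for that difference.* The Wilson limits are 9.6% to 47.3% for 4/17 and 1.0% to 27.0% for 1/17.
  - Lower: 0.176 - √[(0.235 - 0.096)² + (0.270 - 0.059)²] = 0.176 - 0.253 = -0.077.
  - Upper: 0.176 + √[(0.473 - 0.235)² + (0.059 - 0.010)²] = 0.176 + 0.242 = +0.419 (computed from unrounded limits).

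**3. Miss rate of a four-group test, under assumed rates.** For counts x₁…x₄ with mean x̄ and p̄ = x̄/17, the statistic is Σ(xᵢ - x̄)² / [17·p̄(1 - p̄)], compared with 7.81. The miss rate is the total binomial probability of non-significant outcomes over all 18⁴ possible results.

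| Assumed rate: saline / 2.5 / 5 / 10 mg/ml | Harm missed |
|---|---|
| 5/20/20/20% | 84% |
| 10/30/30/30% | 77% |
| 5/10/20/30% | 60% |
| 5/5/15/30% | 49% |
| 5/40/40/40% | 31% |
| 5/10/25/50% | 15% |
| 5/50/50/50% | 9% |

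With a 5% saline rate, 80% detection needs about 38% in a single active arm, or about 45% in all three.

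**4. Would an ordered test be better?** A 1-df dose-trend test (scores 0 to 3) against the four-group test, miss rates under assumed rates:

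| Assumed rates | Trend | Four-group |
|---|---|---|
| 5/10/20/30% | 40% | 60% |
| 5/40/40/40% | 43% | 31% |
| 5/40/30/20% | 93% | 45% |
| 5/30/20/10% | 99% | 60% |

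The trend test gains only if harm rises with strength. The background on clinical experience links atrophy to injecting too great a volume, and to wrong depth. The study procedures cap every active arm at 30 mg per month, so the maximum volumes are 30/2.5 = 12 ml, 30/5 = 6 ml and 30/10 = 3 ml. Maximum volume falls as strength rises, so a dose-ordered pattern cannot be taken for granted.

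**The case against.** The best defence is that the plan does not let a p-value alone decide whether treatment is safe. The safety sentence begins with a summary, the Assessment of Safety section is wholly descriptive, the degree of atrophy is recorded, event intensity is graded, and safety data are reviewed as they arrive. A reader might infer that a non-significant test will be taken as equal safety, or that an acceptable profile at the interim means p > 0.05. No section says either. This part of the defence stands: the misreading is a risk that the plan leaves open, not a rule that it sets.

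A reader might also infer from the upper rows of the table that the test misses a relevant harm in about half to five-sixths of trials. That range is not a property of the plan. The background says that atrophy often accompanied regrowth, without a percentage, so rates of 40 to 50% cannot be ruled out, and there the four-group test misses far less. This stands too.

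On the interim verdict, the Data and Safety Monitoring Plan says that efficacy and safety parameters will be put in place. Their values are not given, but that is detail still to be supplied rather than evidence of a faulty rule.

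Finally, this is called a pilot study, and sizing on efficacy alone is ordinary. That is true, but it argues for estimation with intervals. It does not answer the absence of any measure of precision or the conditional safety comparison.

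**Conclusion.** The point holds as a gap in the analysis method. The plan tests adverse-event incidence in four arms of 17 without any measure of precision, and makes the between-strength safety comparison depend on a significant four-group result.

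The firm part needs no assumed event rate: a non-significant comparison can coexist with an interval reaching +42 points, and an arm with no events still allows a true rate of 16 to 20%. Such results cannot show equal safety.

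The part on missed harm is conditional on assumed rates, a chi-squared test and alpha 0.05. Excesses of about 15 to 25 points are missed in roughly half to 84% of trials in the scenarios tabulated, while much larger excesses are mostly detected. The conclusion should be quoted with that range and not as a single miss rate.

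**What to change.** In the Data Analysis Plan, replace the safety sentence with text to this effect:

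- For skin atrophy and the main adverse-event categories, report incidence per arm with an exact 95% confidence interval.
- Report risk differences with Newcombe 95% intervals for each strength against saline and for each pair of strengths, whatever the result of the efficacy comparison.
- State that a non-significant safety comparison will not be reported as evidence of safety or of equal safety.

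Do not add a Cochran-Armitage trend test as the signal for atrophy; step 4 of the check shows that it can do much worse than the unordered test if harm follows volume.

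The cost is a few sentences and some extra tables: six risk differences per category, best restricted to the main categories. No new patients or data are needed. The downside is wide intervals. By 1.96·√{[p₁(1 - p₁) + p₂(1 - p₂)]/17}, the half-width is about 20 points at 10% v 10% and 26 points at 10% v 30%. Dose safety will therefore be called inconclusive more often than a bare p-value would suggest.
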